#### 8.5 Additional Efficacy Analyses

No additional efficacy analyses are planned.

## 8.6 Efficacy Subgroup Analyses

Subgroup analysis for the primary endpoint will be conducted by the subgroups specified in Table 2. The difference in the primary efficacy endpoint between the treatment groups in each subgroup will be assessed using MMRM method.

Subgroup Factor	Categories		
Age	18 - < 40 years old 40 - < 65 years old $\ge 65$ years old		
Sex	Male Female		
BMI	< 25 ≥ 25		
Race	White Black Asian Other		
Baseline Rheumatoid Factor Status	Positive Negative		
Baseline Anti-CCP Antibody Status	Positive Negative		
Baseline DAS28 (CRP)	> 5.1 ≤ 5.1		
No. of prior anti-TNF biologics	$\begin{array}{c} 0 \ 1 \\ \geq 2 \end{array}$		
Use of non-anti-TNF biologics	YES NO		
Number of prior bDMARD received	$ \begin{array}{c} 1\\ 2\\ 3\\ \geq 4 \end{array} $		
Duration of RA diagnosis	< 6 Months 6 Months - < 1 Year 1 Year - < 3 Years ≥ 3 Years		

#### Table 2.Subgroups for Primary Efficacy Analysis

## 9.0 Safety Analyses

## 9.1 General Considerations

Safety analyses will include reporting of adverse events, laboratory, and vital signs measurements. Safety analyses will be carried out using the Safety Analysis Set.

The following summary statistics will be presented for subjects who have both baseline and post-baseline values for laboratory parameters and vital signs: the mean value at Baseline and at each respective protocol specified visit, and the mean, standard deviation and median for changes from Baseline. Categorical data will be summarized using frequencies and percentages. The number of non-missing values will be given. Missing safety data will not be imputed.

A subject's actual treatment will be determined by the most frequent dose regimen received.

## 9.2 Adverse Events

Adverse events (AEs) will be summarized and presented using primary MedDRA System Organ Classes (SOCs) and preferred terms (PTs) according to the version of the MedDRA coding dictionary used for the study at the time of database lock. The actual version of the MedDRA coding dictionary used will be noted in the AE tables and in the clinical study report. Specific adverse events will be counted once for each subject for calculating percentages, unless stated otherwise. In addition, if the same adverse event occurs multiple times within a subject, the highest severity and level of relationship to investigational product will be reported.

## 9.2.1 Treatment-Emergent Adverse Events

A treatment-emergent Adverse Event (TEAE) is defined as an adverse event with an onset date that is on or after the first dose of study drug, and no more than 30 days after the last dose of study drug; or an adverse event with onset date before the first dose of study drug,

but increased in severity on or after the first dose of study drug, and no more than 30 days after the last dose of study drug.

Events where the onset date is the same as the study drug start date are assumed to be treatment-emergent. If an incomplete onset date was collected for an adverse event, the event will be assumed to be treatment-emergent unless there is other evidence that confirms that the event was not treatment-emergent (e.g., the event end date was prior to the study drug start date).

The number and percentage of subjects experiencing TEAEs will be summarized.

### 9.2.2 Adverse Event Overview

An overview of AEs will be presented consisting of the number and percentage of subjects experiencing at least one event for each of the following AE categories:

- All TEAEs
- Treatment-emergent serious adverse events (SAEs)
- Treatment-emergent severe adverse events
- TEAEs reasonably possibly related to study drug
- TEAEs of special interest (AESIs)
- TEAEs leading to discontinuation of study drug
- TEAE leading to death
- All deaths

Additional AEs may be considered for tabulation/summary based on recommendations from Clinical and Safety as deemed appropriate.

For AESIs, the point estimate and 95% CI (using normal approximation) will be provided for the treatment difference in AE percentages.

## 9.2.3 Treatment-Emergent Adverse Events by SOC and/or PT

The number and percentage of subjects experiencing adverse events will be tabulated by SOC and MedDRA PT by "as treated" treatment groups and overall. The SOCs will be presented in alphabetical order, and the PTs will be presented in alphabetical order within each SOC.

The following summaries of adverse events will be generated:

- All TEAEs
- Treatment-emergent serious adverse events (SAEs)
- Treatment-emergent severe adverse events
- TEAEs reasonably possibly related to study drug
- TEAEs leading to discontinuation of study drug
- TEAE leading to death
- Frequent AEs (reported in 2% of subjects or more in any treatment group)

Subjects reporting more than one adverse event for a given MedDRA preferred term will be counted only once for that term (most severe incident for the severity tables and most related incident for the relationship tables). Subjects reporting more than one type of adverse event within a SOC will be counted only once for that SOC. Subjects reporting more than one type of adverse event will be counted only once in the overall total. In addition, if the same adverse event occurs multiple times within a subject, the highest severity and level of relationship to investigational product will be reported. In addition, TEAEs will be summarized by PT and sorted by decreasing frequency for the total active group.

#### 9.2.4 Treatment-Emergent Adverse Events per Patient-Years of Exposure

TEAEs will be summarized by event rate per 100 subject years, defined as

100 \* (Number of TEAEs)/(Total Patient Years)

where total subject years is defined as the sum of the study drug exposure of all subjects normalized by 365.25 and rounded to 1 decimal place.

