5.4 Prior and Concomitant Therapy

Subjects should continue on their stable (\geq 4 weeks prior to the first dose of study drug) background csDMARD therapy, restricted to the following: oral or parenteral MTX (7.5 to 25 mg/week), sulfasalazine (\leq 3000 mg/day), hydroxychloroquine (\leq 400 mg/day), chloroquine (\leq 250 mg/day), and leflunomide (\leq 20 mg/day). Combinations of up to two csDMARDs are allowed except for the combination of MTX and leflunomide.

At any time, the csDMARD dose may be decreased only for safety reasons. Subjects taking MTX should take a dietary supplement of oral folic acid (or equivalent, such as folinic acid) throughout study participation. Folic acid dosing and timing of regimen should be followed according to Investigator's instructions. AbbVie will not provide the csDMARDs (or folic acid, if taking MTX).

Subjects should continue on their stable doses of NSAIDs, acetaminophen/paracetamol, oral corticosteroids (equivalent to prednisone \leq 10 mg/day), or inhaled corticosteroids.

• If taking any of the above on a scheduled basis, they should continue to take them as they did at study entry with no change in dose or frequency, including on study visit days.

- If not taking any of the above at baseline, these should not be initiated.
- If taking any of the above, including low potency analgesics (i.e., tramadol, codeine, hydrocodone, or propoxyphene) at baseline on an as needed (PRN) basis, they should continue to use them for the same reason and same dose each time, but they should not be taken within the 24 hours prior to any study visit to avoid bias in outcome measurements.

In the event of tolerability (or other safety) issues, the doses of these medications may be decreased or discontinued with substitution of another permitted medication from that class. PRN use of inhaled corticosteroids is permitted at any time.

A long-term extension (LTE) study is planned to be conducted under a separate protocol at sites where it is permitted by the local Competent Authority and Ethics Committee. Patient rollover from the initial randomized portion of the study will occur at Week 12 for all patients to assure comparable length of exposure for each different treatment.

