7.4 Statistical Analyses for Safety

All safety analyses will be performed in the safety populations.

Pre-treatment AEs will be summarized separately.

All treatment-emergent adverse events (TEAEs), SAEs, AEs leading to discontinuation, and AESI will be collected during the study. A TEAE is defined as an event with onset or worsening after the first study dose of study drug and within 30 days after the last dose of study drug administration. The number and percentages of subjects experiencing TEAEs will be tabulated using the Medical Dictionary for Drug Regulatory Activities (MedDRA®) system organ class and preferred term. Summaries (including percentages and event per 100 patient-year) of SAEs, deaths, AEs leading to discontinuation, and AESI will be provided as well. For selected laboratory and vital signs parameters, mean change from baseline and percentage of subject with evaluations meeting pre-defined criteria for Potentially Clinically Important values will be summarized.

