Dispense subject dosing diary and at-home temperature monitoring log		×					
Dispense study drug		×		×.	×.		
Review study drug return and perform drug reconciliation			×	×	~	1	
Review at-home temperature monitoring log and reminder to subjects to conduct their weekly at-home temperature monitoring ^d		×	~	~	1	1	

a. Applies only to those subjects who do not enter LTE Study M16-763.

b. As available and if compliant with local TB guidelines in Canada only.

c. Pre-dose collection.

d. As described in Section 6.2.

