## 5.0 Subject Disposition

The number of subjects will be tabulated by country, investigator site and overall for all randomized subjects.

The total number of subjects who were randomized, and treated will be summarized.

A summary of subject accountability will be provided where the number of subjects in each of the following categories will be summarized for each treatment group:

- Subjects randomized in the study;
- Subjects who took at least one dose of study drug;
- Subjects who completed protocol-specified treatment;

- Subjects who prematurely discontinued study drug (all reasons and primary reason);
- Subjects in each analysis population, as applicable;
- Number of subjects who elect to participate in the open label extension Study M16-763.

In addition, the reasons for premature discontinuation (primary reason and all reasons) from the trial and/or from the medication collected from CRF by the following categories will be summarized with frequencies and percentages. Subjects with multiple reasons for premature discontinuation will be counted once in the calculation of the number and percentage of total discontinuations ("Premature Discontinuation").

- Adverse events,
- Lost to follow-up,
- Withdrew consent by subject,
- Lack of efficacy,
- Others.

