## 6.0 Study Drug Duration and Compliance

A summary of study drug duration (days) will be provided by each treatment arm for the Safety populations.

The duration of exposure to study drug will be summarized for each group as specified above, with the number of subjects, mean, standard deviation, median, minimum and maximum values. In addition, the number and percentage of subjects exposed to study drug will be summarized for the following cumulative duration intervals.

- $\geq 1 \text{ day}$
- $\geq 15 \text{ days}$
- $\geq 29 \text{ days}$
- $\geq 57 \text{ days}$
- $\geq 85 \text{ days}$

The exposure to study drug is calculated as:

Exposure = (date of last study medication – date of first study medication + 1)

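### The TEAE rate per 100 patient-years counts events to 30 days after the last dose but divides by first-to-last-dose time only, so it runs high, and more so in arms with more early stops

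*SAP*

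**What the plan says.** The numerator is the number of TEAEs. SAP 9.2.1 treats an event as treatment-emergent if its onset, or its worsening, falls on or after the first dose and "no more than 30 days after the last dose of study drug". Protocol 7.4 sets the same limit: "within 30 days after the last dose of study drug administration".

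The denominator is total patient-years. SAP 9.2.4 says that "total subject years is defined as the sum of the study drug exposure of all subjects", divided by 365.25 and rounded to one decimal. SAP 6.0 defines exposure as "date of last study medication – date of first study medication + 1". Neither section adds the 30 days after the last dose, and neither limits the rate's numerator to events on drug.

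Follow-up after the last dose is not the same for everyone. Protocol 6.1 collects AEs until 30 days after study drug is stopped. Protocol 5.6 asks that subjects who stop early stay in scheduled follow-up. The 30-day follow-up visit in protocol Appendix D carries the footnote "Applies only to those subjects who do not enter LTE Study M16-763". On the extension, protocol 5.4 says "Patient rollover from the initial randomized portion of the study will occur at Week 12 for all patients", at sites where local bodies permit it; SAP 5.0 treats entry as the subject's choice ("Number of subjects who elect to participate in the open label extension Study M16-763"). Neither document says whether this study's TEAE count closes at the first extension dose.

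**The concern.** A rate per patient-year is used so that arms with unequal time at risk can be compared. That works only if the events and the time come from the same window. Here each subject may contribute up to 30 days in which events count and time does not. In a 12-week study 30 days is 30/84 = 36% of planned treatment, so the gap is not a rounding matter.

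The gap also depends on exposure. The same 30-day tail is set against a shorter denominator when a subject stops early. An arm with more early stops would show a higher rate at equal risk, which is the distortion that exposure adjustment is meant to remove. Protocol 7.4 promises events per 100 patient-years for SAEs, deaths, AEs leading to discontinuation and AESIs, so the definition is likely to carry into those summaries too.

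**Working it through.** The plan states no AE rate, patient-year total, early-stop rate or rollover rate, so there is no figure of its own to reproduce.

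**Inputs from the documents:** treatment 12 weeks = 84 days; event window to last dose + 30 days; exposure = last dose − first dose + 1; planned arms of 60, 40 and 20.

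**Formula.** Let E be exposure days, F the days after the last dose in which events are counted (at most 30 per subject), and f the ratio of the off-drug to the on-drug hazard.
- SAP rate / matched-window rate = (E + F)/E, whatever the event rate.
- SAP rate / on-drug rate = (E + fF)/E. With f = 1 (constant hazard) the two factors are equal.

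**Single subject, full 30-day tail:**

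| Last dose | f = 1 | f = 0.5 |
|---|---|---|
| Day 84 | 114/84 = 1.36 | 99/84 = 1.18 |
| Day 28 | 58/28 = 2.07 | 43/28 = 1.54 |
| Day 14 | 44/14 = 3.14 | 29/14 = 2.07 |

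At f = 0 no events fall in the tail and the factor is 1.00.

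**Patient-years if all complete 84 days with a full tail** (n × 84/365.25, then n × 114/365.25): 13.8 against 18.7 for the arm of 60, 9.2 against 12.5 for an arm of 40, and 4.6 against 6.2 for placebo.

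**Two arms with equal true risk.** All shares are assumed. Arm A: 20% stop at Day 28, 10% complete without rollover, 70% roll over. Arm B: 5%, 5% and 90%.
- Mean exposure, A: 0.80 × 84 + 0.20 × 28 = 72.8 days.
- Mean exposure, B: 0.95 × 84 + 0.05 × 28 = 81.2 days.

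Reading 1, SAP 9.2.1 taken literally: every subject, including rollovers, has a 30-day tail.
- A: (72.8 + 30)/72.8 = 1.412
- B: (81.2 + 30)/81.2 = 1.369
- Spurious rate ratio: 1.412/1.369 = 1.03

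Reading 2: rollover subjects' events stop counting at Week 12.
- A: mean tail 0.30 × 30 = 9 days; 81.8/72.8 = 1.124
- B: mean tail 0.10 × 30 = 3 days; 84.2/81.2 = 1.037
- Spurious rate ratio: 1.124/1.037 = 1.08

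With f = 0.5, the SAP rates have these ratios:
- Reading 1: (87.8/72.8)/(96.2/81.2) = 1.02
- Reading 2: (77.3/72.8)/(82.7/81.2) = 1.04

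**The case against.** The strongest reply is that little depends on this rate. SAP 9.2.4 gives it without a confidence interval or test. The overview and the SOC/PT tables use numbers and percentages of subjects, and the 95% intervals for AESI differences are on percentages; none of them uses this denominator. Sampling error is also much larger than the bias. Suppose a true rate of 200 per 100 patient-years (assumed), with arm A of 60 and arm B of 40 under reading 2. The events are then about 2 × 60 × 81.8/365.25 = 27 and 2 × 40 × 84.2/365.25 = 18. The 95% limits on a Poisson rate ratio lie a factor of exp(1.96 × √(1/27 + 1/18)) = 1.8 either side. This stands, and it is why the point is minor.

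It is also fair to say that the two-fold and three-fold factors describe single subjects. Arm rates pool exposure, so a few early stops move them much less.

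A reader might infer that arms with fewer extension rollovers are shown to get inflated rates, and take 1.08 as the size. The documents do not support that. The Appendix D footnote says who attends a visit, not which events are counted. Taken literally, SAP 9.2.1 has no cut at the extension, so rollovers carry the same tail as other completers and the rollover difference disappears. The extension protocol is separate and not available here. Non-rollover caused by local permission is a site matter, balanced across arms in expectation by randomisation.

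What the reply does not remove is the mismatch itself, or its dependence on early stopping under either reading.

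**Conclusion.** Wrong as written, minor. The two windows differ on the face of SAP 6.0, 9.2.1 and 9.2.4. The direction is certain: the stated rate cannot be lower than the matched-window rate or the on-drug rate.

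The size in this trial cannot be fixed. For a completer with a full tail, the excess over the on-drug rate runs from nothing (no hazard off drug) to 36% (constant hazard). Between arms, the illustration gives a spurious ratio of about 1.03 on the literal text and about 1.08 on the Week 12 cut, at constant hazard. Both rest on assumed early-stop shares of 20% versus 5% at Day 28, and the second also on assumed rollover of 70% versus 90% of all subjects. A larger early-stop imbalance or earlier stops would raise these figures; a lower off-drug hazard would reduce them.

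It would go too far to infer that the trial's safety comparison as a whole is biased: the percentage tables are unaffected.

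**What to change.** In SAP 9.2.4 only, define one window for both parts of the rate: from first dose to the earliest of last dose + 30 days, first dose in M16-763, or last contact. Count TEAEs with onset or worsening in that window and divide by the sum of the same days/365.25. Apply this to every per-100-patient-year summary promised in protocol 7.4. It also settles how rollover subjects are handled in the rate.

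Leave the TEAE definition in SAP 9.2.1 and protocol 7.4 as it is. Cutting TEAEs themselves at the first extension dose would put the SAP in conflict with the protocol and could change every TEAE table. Leave the exposure summary in SAP 6.0 unchanged as well.

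The cost is one definition; no new visits are needed, and the dosing and event dates are already collected. Stated rates become lower, and the rate's event count may differ slightly from the TEAE tables, which a footnote can explain. The matched rate averages time on drug with the 30 days after it, and the footnote should say so.

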## 9.2.5 SAEs (Including Deaths) and Adverse Events Leading to Study Drug Discontinuation

All serious adverse events (SAEs), deaths, and adverse events leading to discontinuation of study drug will be listed. The number and percentage of subjects experiencing SAEs (including deaths) and adverse events leading to discontinuation of study drug will be tabulated by SOC and PT or each treatment group.

## 9.2.6 Adverse Events of Special Interest

The Adverse Events of Special Interest (AESI) categories will be summarized and presented by "as treated" treatment group and overall using SOC and MedDRA PT. The AESI categories will be identified by the following search criteria per Standard MedDRA Queries (SMQs)/Company MedDRA Queries (CMQs) in Appendix B.

## 9.2.7 Adverse Events by Maximum Severity

TEAEs will also be summarized by maximum severity by "as treated" treatment group and overall. If a subject has an AE with an unknown severity, then the subject will be counted in the severity category of unknown, even if the subject has another occurrence of the same event with a severity present. The only exception is that if the subject has another occurrence of the same AE with the most extreme severity – severe. In this case, the subject will be counted under the severe category.

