- Mild (Grade 1): asymptomatic or mild symptoms; clinical or diagnostic observations only; intervention not indicated.
- Moderate (Grade 2): minimal, local or noninvasive intervention indicated; limiting ageappropriate instrumental activities of daily living (ADL) (instrumental ADL refer to preparing meals, shopping for groceries or clothes, using the telephone, managing money, etc.).
- Severe (Grade 3): Severe or medically significant but not immediately life-threatening; hospitalization or prolongation of hospitalization indicated; disabling; limiting self care ADL (self care ADL refer to bathing, dressing and undressing, feeding self, using the toilet, taking medications, and not bedridden);
- Life-threatening (Grade 4): urgent intervention indicated or death related to AE.

The investigator will use the following definitions to assess the relationship of the AE to the use of study drug:

Reasonable Possibility – After consideration of factors including timing of the event, biologic plausibility, clinical judgment, and potential alternative causes, there is sufficient evidence (information) to suggest a causal relationship.

No Reasonable Possibility – After consideration of factors including timing of the event, biologic plausibility, clinical judgment, and potential alternative causes, there is insufficient evidence (information) to suggest a causal relationship.

Pregnancy

While not an AE, pregnancy in a study subject must be reported to AbbVie within 1 working day after the site becomes aware of the pregnancy. Subjects who become pregnant during the study must be discontinued (Section 5.5).

Information regarding the pregnancy and the outcome will be collected.

The pregnancy outcome of an elective or spontaneous abortion, stillbirth or congenital anomaly is considered a SAE and must be reported to AbbVie within 24 hours after the site becomes aware of the event.

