## 9.3 Analysis of Laboratory Data

Data collected from central and local laboratories, including additional laboratory testing due to an SAE, will be used in all analyses, except for Baseline, where SAE-related laboratory assessments on or before the first dose of study drug will be excluded. The

clinical laboratory tests defined in the protocol operations manual (e.g., hematology and clinical chemistry) will be summarized.

Mean change from baseline to each applicable post-baseline visit will be summarized for selected laboratory variables, with the number of observations, baseline mean, and visit mean. The change from baseline mean, standard error, and 95% confidence interval will be presented for the mean change from baseline within each treatment group and difference between treatment groups using ANOVA model.

The baseline and post-baseline laboratory observations will be categorized as Grade 1, Grade 2, Grade 3, and Grade 4 according to OMERACT criteria (Rheumatology Common Toxicity Criteria v.2.0). For creatine phosphokinase and creatinine, NCI CTC criteria will be used.

For each laboratory variable, shift tables will be generated that cross tabulate the subjects' as deemed appropriate by "as treated" treatment group:

- Category of the baseline value versus category of the final value.
- Category of the baseline value versus maximum category.
- Category of the baseline value versus minimum category.

Note that the minimum/maximum category is used, rather than the category of the minimum/maximum value. The two may be different due to variation in the reference range.

No statistical tests will be performed for this analysis.

Laboratory abnormalities will be evaluated based on Potentially Clinically Significant (PCS) criteria (Appendix C). For each laboratory PCS criterion, the number and percentage of subjects who have a laboratory value meeting the criteria will be summarized. Listings will be provided to summarize subject-level laboratory data for subjects meeting PCS criteria.

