J3. Dyspnea	Subjective, transient, no interference with function	Symptomatic, intermittent or recurring, interferes with exertional activities	Symptomatic during daily routine activities, interferes with function, treatment with intermittent nasal O 2 relieves	Symptomatic at rest, debilitating, requires constant nasal O 2
J4. Pleuritic pain (pleurisy)	Transient, intermittent symptoms, no treatment or OTC meds relieve	Persistent symptoms, requires prescription meds for relief	Prolonged symptoms, interferes with function, requires frequent narcotic pain relief	Debilitation, requiring hospitalisation
J5. Pneumonitis (pulmonary infiltrates)	Asymptomatic radiographic changes, transient, no treatment required	Symptomatic, persistent, requiring corticosteroids	Symptomatic, requiring treatment including O 2	Debilitating, not reversible; or requiring assisted ventilation
J6. Pulmonary function decreased (FVC or carbon monoxide diffusion capacity – DLCO)	76% – 90% of pre- treatment value	51% – 75% of pre- treatment value	26% – 50% of pre- treatment value	$\leq 25\%$ of pre- treatment value

Laboratory Data					
K. Haematology					
K1. Hgb (g/dl) decrease from pre-treatment	1.0 - 1.4	1.5 - 2.0	2.1 – 2.9, or Hgb < 8.0, > 7.0	$\geq$ 3.0; or Hgb < 7.0	
K2. Leukopenia (total WBC) × 1000	3.0 - 3.9	2.0 - 2.9	1.0 - 1.9	< 1.0	
K3. Neutropenia (× 1000)	1.5 – 1.9	1.0 - 1.4	0.5 - 0.9	< 0.5	
K4. Lymphopenia (× 1000)	1.5 – 1.9	1.0 - 1.4	0.5 - 0.9	< 0.5	
K5. Platelets (× 1000)	75 – LLN	50 - 74.9	20 – 49.9; platelet transfusion required	< 20; recurrent platelet transfusions	
L. Chemistry					
L1. Hypercalcaemia (mg/dl)	1.1 × ULN – 11.5	11.6 - 12.5	12.6 – 13.5; or symptoms present	> 13.5; or associated coma	
L2. Hyperglycemia (mg/dl) Fasting	140 - 160	161 – 250	251 - 500	> 500, or associated with ketoacidosis	
L3. Hyperkalaemia (mmol/l)***	5.5 - 5.9	6.0 - 6.4	6.5 – 7.0 or any ECG change	> 7.0 or any arrhythmia	
L5. Hypocalcaemia (mg/dl)	0.9 × LLN – 7.8	7.7 – 7.0	6.9 – 6.5; or associated with symptoms	< 6.5 or occurrence of tetany	
L6. Hypoglycemia (mg/dl)	55 – 64 (no symptoms)	40 – 54 (or symptoms present)	30 – 39 (symptoms impair function)	< 30 or coma	
L7. Hyponatraemia (mmol/l)***	-	125 – 129	120 – 124	< 120	
L8. Hypokalaemia (mg/dl)***	-	3.0 - 3.4	2.5 - 2.9	< 2.5	
L9. CPK (also if polymyositis-disease)****	> ULN – 1.5 × ULN	$> 2.5 - 5.0 \times ULN$ $> 5.0 - 10.0 \times ULN$		> 10.0 × ULN	

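### Two SAP safety-grading rules do not work as written: CPK above 1.5 and up to 2.5 × ULN has no grade, and the maximum-severity rule stops at severe although Grade 4 lies above it

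*SAP*

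**What the plan says.** **CPK.** SAP 9.3 sorts baseline and post-baseline laboratory values into Grades 1 to 4 by the OMERACT table, with one substitution: "For creatine phosphokinase and creatinine, NCI CTC criteria will be used". Table C-1 prints the substituted limits in the row labelled "L9. CPK (also if polymyositis-disease": Grade 1 above ULN to 1.5 × ULN, Grade 2 above 2.5 to 5.0, Grade 3 above 5.0 to 10.0, Grade 4 above 10.0. The grades feed the shift tables in 9.3. Appendix C also bases the potentially clinically significant (PCS) laboratory criteria on Table C-1. No NCI CTC version is named.

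**Severity.** Protocol 6.1 has investigators grade adverse events by the Rheumatology Common Toxicity Criteria (Appendix F), with a four-level fallback where that table has no entry. In the fallback, Grade 3 is severe but short of an immediate threat to life. The level above it reads "Life-threatening (Grade 4): urgent intervention indicated or death related to AE". Table C-1 of the SAP has the same fourth column.

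SAP 9.2 gives the general rule for repeated events: "the highest severity and level of relationship to investigational product will be reported". SAP 9.2.7 adds a rule for missing grades. With one ungraded occurrence, "the subject will be counted in the severity category of unknown, even if the subject has another occurrence of the same event with a severity" recorded. The only exception is "another occurrence of the same AE with the most extreme severity", which the SAP names as severe. The overview in 9.2.2 has a row for "Treatment-emergent severe adverse events", repeated by system organ class and preferred term in 9.2.3. Neither section maps that label to a grade.

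**The concern.** A grading table must give every abnormal value one grade, and a worst-case rule must let the worst category win. Row L9 fails the first test and 9.2.7 fails the second.

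For CPK, a programmer meeting 2.0 × ULN has to invent a treatment: leave it ungraded, add it to a neighbouring grade, or set it to missing. Each choice gives a different shift table.

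For severity, the rule protects a Grade 3 event from being hidden by an ungraded recurrence but does not protect a Grade 4 event. Separately, two programmers could count different subjects in the severe rows, depending on whether they read the word as Grade 3 or as Grade 3 and above. Safety is part of the main objective, and the combination is new, so these tables should be reproducible from the text.

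**Working it through.** The plan states no figure to reproduce. The check is whether the rules cover every case, so I applied them literally.

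**CPK.** Inputs: row L9 of SAP Table C-1 and row L9 of protocol Appendix F (Grade 1 from 1.2 to 1.9 × ULN, Grade 2 from 2.0 to 4.0 × ULN).

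| CPK (× ULN) | SAP Table C-1 | Protocol Appendix F |
|---|---|---|
| 1.2 | Grade 1 | Grade 1 |
| 1.5 | Grade 1 | Grade 1 |
| 1.51 | none | Grade 1 |
| 1.9 | none | Grade 1 |
| 2.0 | none | Grade 2 |
| 2.5 | none | Grade 2 |
| 2.51 | Grade 2 | Grade 2 |
| 5.1 | Grade 3 | depends on symptoms |
| 10.1 | Grade 4 | depends on symptoms |

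The ungraded interval is (1.5, 2.5] × ULN, of width 2.5 − 1.5 = 1.0 × ULN. The value 1.5 itself is graded. Grades 2 and 3 meet at 5.0, and Grades 3 and 4 meet at 10.0, so the gap is the only break in the row above ULN.

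The consequence for the shift from baseline to maximum category: a subject at 1.5 × ULN at Week 4 and 2.0 × ULN at Week 8 has Grade 1 at the lower value and nothing at the higher one. If ungraded values are ignored, the maximum category is Grade 1 and the higher reading leaves no trace.

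The other row replaced by NCI CTC limits, L11 creatinine, is contiguous in its ULN limits (1.5, 3.0 and 6.0 × ULN). The gap is therefore specific to L9.

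**Severity.** Input: the rule in 9.2.7, with severe taken as the protocol's Grade 3.

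| Occurrences of one event in one subject | Result under 9.2.7 |
|---|---|
| ungraded + Grade 2 | unknown |
| ungraded + Grade 3 | severe |
| ungraded + Grade 4 | unknown |
| ungraded + Grade 3 + Grade 4 | severe |

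The third line is the anomaly: the worse event is hidden where the milder one in line two is not. In line four the Grade 4 occurrence appears only as severe.

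SAP 9.2.8 uses the same construction for relationship to study drug. There the category that overrides unknown is the higher of the protocol's two levels, so the rule works. For severity, the category named as the top is not the top of the scale.

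**The case against.** The strongest reply on severity is that 9.2.7 plainly means the worst category to override unknown. If the SAP has a three-level scale in mind, Grade 4 sits inside severe and nothing is lost. That is the more natural intention, and it limits the charge to an undefined mapping. It does not remove the charge: the protocol's Grade 3 excludes immediately life-threatening events, the SAP's own table has a fourth column, and no sentence merges Grades 3 and 4.

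Several stronger readings are tempting, and the documents do not support them:

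- *The worst events drop out of the safety report.* Deaths and life-threatening events meet the SAE criteria in protocol 6.1. SAP 9.2.2, 9.2.3, 9.2.5 and 9.2.11 tabulate or list SAEs, events leading to death and all deaths.
- *Every Grade 4 or fatal event is affected.* The unknown rule needs an ungraded occurrence of the same event in the same subject.
- *The severe rows hold Grade 3 only.* The SAP does not say so; it leaves the point open.
- *9.2.7 contradicts 9.2.* It is better read as a specific exception for missing grades.
- *CPK counts of special interest are wrong.* Appendix B finds those by the preferred term for increased blood CPK, not by grade.
- *Management under the protocol is affected.* The CPK threshold in protocol Table 4 is ≥ 4 × ULN, above the gap.

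A fault in reading the PDF is possible in principle. It is unlikely, because the row is legible and its other limits meet exactly.

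**Conclusion.** Both defects stand, with limited reach.

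The CPK gap follows from the printed limits and needs no assumption. It affects the grade categories and shift tables of SAP 9.3, and any PCS count based on grade. The last effect is uncertain because the SAP does not say which grade triggers a PCS count. How many subjects would fall in the gap cannot be derived: the documents give no CPK distribution.

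The severity defect has two parts. The undefined label affects the severe rows in 9.2.2 and 9.2.3 whenever a Grade 4 event occurs. The unknown rule matters only when an ungraded and a Grade 4 occurrence of the same event coincide in a subject, and it rests on a literal reading of 9.2.7.

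A reader might infer that the Grade 1 upper limit was meant to be 2.5 × ULN. That would close the gap, but so would lowering the start of Grade 2. Without a named NCI CTC version, the documents do not show which limit is wrong.

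Nothing here touches the primary endpoint, the reporting of SAEs and deaths, or the CPK search for events of special interest. This is a correction worth making, not a threat to the trial's conclusions.

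**What to change.** 1. In Table C-1 row L9, make the Grade 1 upper limit and the Grade 2 lower limit meet, by reconciling the row with the NCI CTC version actually used. Name that version in SAP 9.3 and in the note to the table.
2. In SAP 9.2.2 and 9.2.3, define severe as Grade 3 or higher.
3. In SAP 9.2.7, tabulate maximum grade from 1 to 4, and let a Grade 3 or Grade 4 occurrence override unknown, with the higher of the two shown.

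The cost is a few words in three SAP sections, one reconciled limit in a table row, and a version reference. No new data are needed. The changes are best made before unblinding, so that the tables do not depend on choices made with the treatment groups in view.
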